6.2 Data Quality and Confidentiality

The information obtained during this study will remain confidential and will be stored in a file cabinet with a key lock. [name] and [name] the Sub- investigators of this study under the supervision of the Principle Investigator [name] will be responsible for the following:

- 1). Explaining the study to potential participants along with conducting the consent process with the patient.
- 2). Asking related questions to consented participants regarding the research information obtained during the conduction of this study.
- 3). The medical review of patient health information determine eligibility.
- 4). Administration of the vapocoolant spray and placebo spray prior to IV access.
- 5). Performing IV access on study participants
- 6). Identifying any adverse reaction to the intervention being used. All adverse events will be reported to and managed by the Principle Investigator.

These responsibilities performed only by the Sub Investigators will ensure that there will be no threat to the validity of the study being performed and its study results. Data for this study will be kept only as long as the study is being conducted and analyzed for results. Once this information has been obtained all records will be discarded in accordance with hospital policy and applicable regulations. Within the consenting process the patient will be made aware that their information will be kept confidential and that the patient has the right to end their participation in the study at any point.

6.3 Regulatory and Ethical Considerations

6.3.1 Risk Assessment

Adverse events with these products are uncommon. The interventional products being used have been tested and studied for any adverse reactions. Sterile water can will be cooled in a refrigerator to “mimic” a cooling sensation when applied to the patient’s skin. The only foreseeable risk would be the perceived “cold” by the patient. Because the sterile water is sterile there is no risk to contamination of the skin after the researcher has applied the aseptic technique for accessing an intravenous catheter. The Gebauer Company, the manufacturer of the interventional vapocoolant ethyl chloride spray has indicated that it is extremely rare to have an adverse reaction to the ethyl chloride however cutaneous sensitization may occur. Freezing can occasionally alter skin pigmentation. A study has been published in the Journal of Hospital Infection titled the “Effects of vapocoolant spray on skin sterility prior to intravenous cannulation” which concluded that vapocoolant spray does not recontaminate the skin after disinfection, and should pose no increased risk of infection when used as an anesthetic agent prior to intravenous cannulation. (Evans, J.G., Taylor, D.M., Hurren, F., Ward, P., Yeoh, M., & Howden, B.P., 2015).

The Gebauer Company list precautions when using the ethyl chloride spray specifically stated as: Do not spray in eyes. Inhalation of ethyl chloride should be avoided as it may produce narcotic and general anesthetic effects, and may produce deep anesthesia or fatal coma with respiratory or cardiac arrest. Ethyl chloride is flammable and should never be used in the presence of an open flame or electrical cautery equipment. When used to produce local freezing of tissues, adjacent skin areas should be protected by an application of petroleum. The thawing process may be painful, and freezing may lower local resistance to infection and delay healing. (Gebauer's Ethyl Chloride Spray, 2016).

The sub investigators for the study will monitor the patient for any potential reaction to the ethyl chloride spray. The most common reaction being temporary skin color changes at the spray site. Furthermore, the sub investigators will monitor for the very rare but severe allergic reactions that could occur including rash; hives; itching; difficulty breathing; tightness in the chest; swelling of the mouth, face, lips, or tongue; decreased urination; symptoms of liver problems (eg, dark urine; loss of appetite; pale stools; stomach pain; unusual nausea or tiredness; yellowing of the skin or eyes). (Gebauer's Ethyl Chloride Spray, 2016). (See Attachment 6- The Gebauer Company's Safety Data Sheet (SDS).

6.3.2 Potential Benefits of Study Participation

The benefit to the patient who receives the intervention prior to IV cannulation can result in the possible reduction in pain during the IV access and/or the perception thereof. Knowledge gained from this research may help guide treatment guidelines in the future.

6.3.3 Informed Consent/Assent and HIPPA Authorization

In order to protect human rights this study will be conducted in full conformance with principles of "Declaration of Helsinki" and good clinical practice. This study will comply with all protocols set forth for research at Aultman Health Foundation under the guidance of the HRRB.

7.0 SAFETY MANAGEMENT

7.1 Adverse Events and Collection/Reporting

The patients in this study will remain in the department for at least 2 hours following IV insertion to ensure that the sub investigators of the study have adequate time to monitor the patient pre-and post interventional spray specifically the use of the ethyl chloride spray to ensure no reaction has and/or will occur as it relates to the use of ethyl chloride. In the case that an adverse reaction would occur the Principle Investigator of the study [name] would be contacted to assess and treat the patient for the reaction in question.

7.2 Data Safety Monitoring Plan

The Principle Investigator will be responsible for oversight of this project. All Investigators will be trained on reporting and oversight of regulatory

requirements. Data and outcomes produced by this research study will be monitored by the HRRB office on a regular basis. Data review will occur after the first three (3) patients and every 30 patients thereafter. The study will be registered on clinicaltrials.gov, with regular updates as required by regulations.

8.0 STATISTICAL CONSIDERATIONS

Analysis for this study is a descriptive statistic of a covariance using pre-procedure perception as the covariance. A power analysis was completed and determined that a minimum sample with a level of significance of 0.5 moderate effect size is 30 subjects. Our goal for this study is to exceed that sample size and have up to 80 participants. Statistical assistance will be sought to assure accurate data input and complete data results.

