2.0 STUDY OBJECTIVES

2.1 Primary Objective

The Nuclear Medicine department at Aultman Hospital seeks to address the issue surrounding pain and satisfaction associated with the invasive procedure of starting an intravenous catheter (IV) for the injection of radiopharmaceutical

and/or medications needed to complete nuclear images and provide for viable scans. The primary purpose of this study is to determine if by applying a vapocoolant (cold spray) at the IV insertion site on Nuclear Medicine outpatients will increase the satisfaction with IV insertion as well as determine if pain of insertion is decreased. Furthermore, this study will examine the patients' perception in using a vapocoolant spray as a way to improve upon the traditional method of starting IV's that do not offer pain management prior to their insertion. A sterile water mist will be used as the comparator spray to add validity to the standard of care arm.

Research Questions:

For the purpose of this study, the following questions will be addressed:

1. Will patients perceive a vapocoolant spray to be more effective in reducing pain prior to IV cannulation insertion over saline spray?
2. Will the use of a vapocoolant spray increase satisfaction with insertion at an intravenous site over that of a sterile water spray?

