5.4 Data Collection

The questionnaire (See Attachment 4- Patient Questionnaire and Researcher Documentation Form) will include the following questions prior to the use of the intervention:

- 1.) Using the visual analog scale provided how would you rate your pain the last time you remember having an IV inserted?
- 2.) Using a 0-5 Likert scale please rate how satisfied you were the last time you remember having an IV inserted?
- 3.) Do you think it is important to control the pain of starting an IV?

Once the IV has been placed the researcher will ask the patient the following questions:

- 1.) Using the same 0-10 pain scale how would you rate this IV insertion?
- 2.) Using the same 1-5 satisfaction scale how satisfied were you with this IV insertion?
- 3.) Would you choose to have a spray used again if you needed to have an IV inserted in the future?

The researcher will document the patient responses as well as the angiocatheter size, angiocatheter location, numbers of IV start attempts, the time that the intervention was applied and what interventional spray was used. (See Attachment 4- Patient Questionnaire and Researcher Documentation Form). This information will be coded and will be used to analyze study results post intervention. The presence of adverse events will be monitored and documented for 120 minutes following the IV insertion.

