6.0 STUDY ADMINISTRATION

6.1 Description of Study Process

This study will be conducted using patients who are ordered to undergo a Nuclear Medicine Stress Test. These patients will only be seen in this department the day that the stress test exam is performed. The anticipated time it will take to gather the patient's information, conduct the recruitment and consent portion of the study is approximately 30 minutes per patient. This study will use a convenience sample of patients over a 4-month period. The target goal is 30 patients; however, researchers may recruit up to 80 patients.

Once the determination has been made by the researcher that the patient is a candidate for the study the patient has consented they will be assigned to either the control group or experimental group through a computerized randomization sheet. Both the control group and experimental group will be equally represented. Once the IV has been placed regardless of what intervention was used the patient will then be asked by the researcher the questions as stated above.

The participants will only have the intervention used on a first attempt IV access. If the participant has to have additional attempts by the researcher to start an IV, their study will automatically be excluded.

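### Section 8.0 misstates the analysis: ANCOVA is probably meant, but no outcome, arm term, matched covariate, effect estimate or test is given

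*Combined protocol and SAP*

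**What the plan says.** Section 8.0 describes the analysis in a single sentence: "Analysis for this study is a descriptive statistic of a covariance using pre-procedure perception as the covariance". It then reports that "A power analysis was completed" and gives the result as "a level of significance of 0.5 moderate effect size is 30 subjects". Its only other remark on analysis is that statistical help will be sought with data entry and results.

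The research questions in Section 2.1 are comparative. The second reads "Will the use of a vapocoolant spray increase satisfaction with insertion at an intravenous site over that of a sterile water spray"; the first asks the corresponding question about pain. Section 5.3 sets up an experimental and a control group. Section 6.1 assigns patients by computer randomization and says "Both the control group and experimental group will be equally represented". On numbers it says "The target goal is 30 patients; however, researchers may recruit up to 80 patients".

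Section 5.4 lists three questions before insertion: recalled pain at the last IV, recalled satisfaction with the last IV, and "Do you think it is important to control the pain of starting an IV". After insertion it asks for pain on a 0-10 scale, satisfaction on a 1-5 scale, and willingness to have a spray again.

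**The concern.** The trial randomizes patients between two sprays and asks whether one does better on pain and on satisfaction. The analysis should therefore estimate a difference between arms for each outcome. The only analysis sentence mentions neither arms nor outcomes and calls itself descriptive, while the next sentence relies on a significance level and an effect size, which belong to a hypothesis test.

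At stake is whether the main comparison is fixed in advance. A later analyst would have to supply the outcome, the covariate, the model and the contrast. Even the contrast is open. The pre-procedure ratings concern a previous IV, and Section 9.0 says the study can also be used to compare the spray with current practice. A within-patient contrast of this IV with the last one would therefore be a possible choice, and it would lose the protection of randomization. Pre-specification matters more than usual here. The study is single blind (Section 5.1), the sub-investigators who apply the spray also collect the ratings (Section 6.2), data are reviewed after three patients and then every 30 (Section 7.2), and enrolment may end anywhere from 30 to 80.

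**Working it through.** **1. What a between-arm analysis must state, against what Section 8.0 states**

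| Element | Section 8.0 | Elsewhere |
|---|---|---|
| Outcome | not named | pain and satisfaction are in the questions (2.1) and data items (5.4), but tied to no analysis |
| Arm term | not named | arms defined in 5.3 and 6.1 |
| Covariate | a pre-procedure perception, unspecified | three pre-procedure items in 5.4 |
| Effect estimate, interval | none | none |
| Test | none; called descriptive | none |

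**2. Which covariate.** Section 5.4 pairs two of the three pre-procedure items with a later rating.

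| Pre-procedure item | Post-insertion counterpart |
|---|---|
| recalled pain | pain, 0-10 |
| recalled satisfaction, printed as 0-5 | satisfaction, 1-5 |
| importance of controlling pain | none |

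That leaves two serious candidates, and the natural pairing is clear but unstated. The satisfaction pair is printed on two different scales, although Section 5.2 describes one scale of 1-5.

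**3. Can the sample size reveal the intended model?** The plan's own figure is 30. Power, sidedness, effect metric and test are not stated, so 30 cannot be reproduced from the documents. The inputs below are assumptions: "moderate effect size" taken as d = 0.5, with 80% power unless noted.

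- Two arms, two-sided 0.05: n per arm = 2(1.960 + 0.842)²/0.5² = 62.8, so 63, total 126 (128 by noncentral t).
- Two arms, 0.5 as printed, two-sided: 2(0.674 + 0.842)²/0.5² = 18.4, so 19, total 38 (36 by noncentral t).
- Two arms, 0.5 as printed, one-sided, 90% power: 2(0 + 1.282)²/0.5² = 13.1, so 14, total 28.
- Paired t, two-sided 0.05: 34.
- Test of a single correlation of 0.5, two-sided 0.05: [(1.960 + 0.842)/atanh(0.5)]² + 3 = (2.802/0.549)² + 3 = 29.01, so 30.

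For a two-arm ANCOVA at two-sided 0.05, f² = (d/2)²/(1 − r²), with a noncentral F on 1 and N − 3 degrees of freedom and noncentrality N·f². The correlation r between covariate and outcome is not in the documents, so a range is shown:

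| r | Total N for 80% power | Power at N = 30 | Power at N = 80 |
|---|---|---|---|
| 0 | 128 | 26% | 60% |
| 0.3 | 118 | 28% | 64% |
| 0.5 | 98 | 33% | 72% |
| 0.7 | 68 | 46% | 87% |
| 0.9 | 28 | 86% | over 99% |

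Several unrelated readings land near 30: a correlation test, an ANCOVA with r near 0.9, and a one-sided test at 0.5 with 90% power. The documents state none of them, so the sample-size sentence does not settle what the analysis sentence means.

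**The case against.** The strongest reply is that this is a garbled sentence and not a wrong analysis. Using one variable as the covariance makes little sense for a simple covariance, but good sense as a slip for a covariate in an ANCOVA. Two randomized arms, between-spray questions and a power analysis all point the same way. This stands as the best reading of intent, and it rules out some stronger inferences:

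- A reader might infer that the sponsor deliberately chose a non-comparative analysis and so cannot answer its questions. That follows only from the literal words. The ANCOVA probably meant would compare the arms, and the data in Section 5.4 would support it.
- A reader might infer that a pre/post covariance is the same whether or not the spray works. That holds only for a constant shift on an unbounded scale. If the spray halved pain, the covariance in that arm would halve too, since cov(X, Y/2) = cov(X, Y)/2, and a bounded 0-10 rating also breaks the equality. A covariance is still not an estimate of a treatment effect.
- A reader might infer from the correlation result of 30 that a pre/post correlation was the planned analysis. The documents do not say so.
- A reader might count three competing covariates. The importance item has no post-insertion counterpart and is not a serious candidate.

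The reply does not supply what is missing. Even with ANCOVA granted, the plan does not state the outcomes, the arm contrast, the covariate for each outcome, the estimate or the test. It is also fair to say that ANCOVA on a five-point rating is one defensible choice among several; what matters is that one is stated beforehand.

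**Conclusion.** The point holds as a misstated and incomplete analysis plan. Section 8.0 probably intends ANCOVA, but as written it does not deliver either between-spray comparison in Section 2.1, no other section does so, and its descriptive label conflicts with the hypothesis-testing language that follows.

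No calculation decides this; it rests on the text. The attachments listed in Section 11.0 are, by title, patient letters, forms, scales and safety sheets, and are assumed to contain no analysis plan. The sample-size figures show only that 30 identifies no model; they depend on the assumed d = 0.5, the assumed power and an unknown r. Nothing in the documents shows that an analysis has been or will be chosen after seeing results; the plan simply does not prevent it. The wording should be corrected before any outcome data are compared by arm.

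**What to change.** Replace the analysis sentence in Section 8.0 with:

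> Post-insertion pain (0-10) will be compared between randomized arms by ANCOVA with arm as factor and recalled prior-IV pain as covariate. Post-insertion satisfaction (1-5) will be compared by the same model with recalled prior-IV satisfaction as covariate. Adjusted mean differences with two-sided 95% confidence intervals and p-values will be reported.

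Two corrections go with it:

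- Put the pre- and post-insertion satisfaction items in Section 5.4 on one scale.
- Correct the printed significance level of 0.5 to two-sided 0.05, so that it agrees with the 95% intervals. If 0.5 was meant as the effect size, say so and state the significance level separately.

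The new text does not say which outcome is primary, or how patients excluded after a failed first attempt (Section 6.1) are handled; both still need a decision. The cost is a wording change, since every variable is already collected. If patients have already answered the satisfaction item on a 0-5 form, record that and how those answers are treated.

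### Section 8.0 prints a significance level of 0.5, and its minimum of 30 gives only about 26% to 46% power for a 0.5 SD difference at two-sided 0.05.

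*Combined protocol and SAP*

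**What the plan says.** Section 8.0 describes the analysis as a covariance analysis "using pre-procedure perception as the covariance". It then says that a power analysis was done and that "a minimum sample with a level of significance of 0.5 moderate effect size is 30 subjects", and adds: "Our goal for this study is to exceed that sample size and have up to 80 participants".

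Section 6.1 turns the figure into a recruitment aim: "The target goal is 30 patients; however, researchers may recruit up to 80 patients". Patients are randomised by computer to two groups: "Both the control group and experimental group will be equally represented". The same section removes some patients after randomisation: "If the participant has to have additional attempts by the researcher to start an IV, their study will automatically be excluded".

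The plan does not state the target power, whether the test is one- or two-sided, a separate numerical effect size, the outcome that was powered (pain or satisfaction), the assumed correlation between the pre-procedure rating and the outcome, or any allowance for patients excluded.

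**The concern.** There are two linked faults in one sentence.

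- **The threshold.** Read as printed, the significance level is 0.5, so a result with a one-in-two probability under no effect would count as significant. Read as a run-together phrase in which 0.5 is the effect size, the significance level is missing. Either way the plan gives no usable threshold.
- **The sample size.** The figure of 30 is credited to a power analysis and called a minimum, yet 15 per arm is small for a moderate between-group difference at a conventional level.

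Section 6.1 still calls 30 the target, so a trial that stopped there would comply with its protocol and could cite the power analysis as its reason. A null result at 30 would say little about whether a moderate effect exists.

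**Working it through.** **Inputs from the documents.** Total N is 30 as minimum and target, and up to 80 (Sections 8.0 and 6.1). Allocation is equal (Section 6.1). The effect is called moderate, and the pre-procedure rating is the covariate (Section 8.0).

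**Assumptions, because the plan gives no figures.** Moderate means d = 0.5 SD. The significance level is 0.05, two-sided, with one-sided also tried. The covariate correlation r is 0, 0.3, 0.5 or 0.7. One outcome is tested at a time, and N is the number analysed.

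**Formula.** Power comes from the noncentral t distribution with noncentrality d × √(N/4) / √(1 − r²). Degrees of freedom are N − 2 without the covariate and N − 3 with it.

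**Step 1: try to reproduce 30.** At d = 0.5 and two-sided 0.05, the total N for 80% power is 128, 118, 98 and 68 at r = 0, 0.3, 0.5 and 0.7. One-sided, the range is 102 (r = 0) to 52 (r = 0.7). None is near 30. With the significance level taken literally as 0.5, N = 30 gives 78%, 79%, 83% and 90% two-sided at the same four correlations.

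**Step 2: power at 30, two-sided 0.05.**

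- r = 0: noncentrality = 0.5 × √7.5 = 1.369; critical t (28 df) = 2.048; power 26.2%.
- r = 0.5: noncentrality = 1.369 / √0.75 = 1.581; critical t (27 df) = 2.052; power 33.2%.
- r = 0.7: noncentrality = 1.369 / √0.51 = 1.917; critical t (27 df) = 2.052; power 45.6%.

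**Step 3: all scenarios (d = 0.5, level 0.05).**

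| Analysed | Test | r = 0 | r = 0.3 | r = 0.5 | r = 0.7 |
|---|---|---|---|---|---|
| 30 | two-sided | 26% | 28% | 33% | 46% |
| 30 | one-sided | 38% | 40% | 46% | 59% |
| 80 | two-sided | 60% | 64% | 72% | 87% |

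A simulation of the covariate-adjusted analysis (20,000 runs, two-sided) gave 32.2% (N = 30, r = 0.5), 44.4% (N = 30, r = 0.7) and 71.7% (N = 80, r = 0.5), in line with the formula.

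**Step 4: what 30 would require.** For 80% power at d = 0.5, r would have to be about 0.88 two-sided or 0.84 one-sided. Without that, the difference detectable with 80% power (two-sided) at 30 is 1.06 SD at r = 0 and 0.92 SD at r = 0.5. At 80 it is 0.634 SD and 0.549 SD. Other effect sizes at 30, unadjusted, give 18.5% (0.4 SD), 35.5% (0.6 SD) and 56.2% (0.8 SD).

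**Step 5: exclusions for further attempts.** The documents give no rate, so 10% to 20% is assumed. Then 30 recruited leave 27 to 24 analysed, with 24% to 22% power unadjusted. And 80 recruited leave 72 to 64, with 55% to 50% unadjusted or 68% to 62% at r = 0.5.

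**The case against.** The sponsor could fairly say the following.

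- **The figure of 30 fits the inputs as printed.** At a level of 0.5 it gives roughly 78% to 90% power two-sided. This stands as arithmetic, and may even mean that 0.5 was entered in the calculation. It does not rescue the plan, because 0.5 is not an acceptable level. Once it is corrected, the support for 30 goes with it.
- **The figure may come from another design.** At 0.05 and d = 0.5, a paired t-test needs 27 (one-sided) to 34 (two-sided) for 80% power, and a test of a correlation of 0.5 needs 30. The plan states neither, and neither is the comparison of two randomised arms that it describes.
- **The trial is meant to go beyond 30.** Section 8.0 aims for up to 80, Section 7.2 schedules data review every 30 patients after the first three, and Section 5.3.1 estimates two cans at up to 50 uses each. This shows that stopping at 30 is permitted rather than planned. Even so, 30 remains both the minimum and the target.
- **The analysis is called descriptive, and the research questions are directional.** The plan still cites a significance level and a power analysis and asks comparative questions. One-sided testing lifts power at 30 only to 38% to 59%.
- **No stated power is contradicted, and the correlation of 0.88 is called too high without data.** Both are true. The plan states no power to contradict. That 0.88 is implausible for a remembered rating of a past IV against today's rating is a judgement.

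**Conclusion.** The concern holds and must be fixed. The plan's only significance level is misprinted or missing, and 30 is not supported as a power-based minimum for the two-arm, covariate-adjusted comparison described. On the stated assumptions, power at 30 analysed is about 26% to 46% two-sided. The conclusion does not depend on sidedness or on any covariate correlation up to 0.7. It would change only if moderate meant a difference of about 0.76 SD or more with r = 0.7 (about 1.06 SD with no covariate), or if the correlation were near 0.88. The permitted maximum of 80 is much better, at 60% to 87%, so the problem lies in the stated minimum and target.

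**What to change.** In Section 8.0, state the significance level as 0.05, two-sided, remove the claim that the power analysis gave 30 as the minimum, and report power by number analysed. Suggested text:

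> Significance level 0.05, two-sided. Assuming a difference of 0.5 SD between two equal arms on [pain or satisfaction, to be named], power is about 26% with 30 analysed and 60% with 80 analysed without covariate adjustment, or 33% and 72% if the pre-procedure rating correlates 0.5 with the outcome. With 80 analysed there is 80% power for about 0.64 SD unadjusted, or 0.55 SD at correlation 0.5. Patients excluded for additional IV attempts reduce these figures (for example, 22% unadjusted with 12 per arm analysed).

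(0.64 is 0.634 rounded up, since 0.63 SD falls just short of 80%.) If the sponsor intends a one-sided test, that should be said and the figures replaced. Whether the 0.05 applies separately to pain and to satisfaction should also be stated.

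In Section 6.1, replace the target of 30 with a statement that recruitment is planned up to 80 and that 30 is not a power-based target.

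The cost is wording in two sections, with no added patients beyond 80, visits or data. The downside is a less favourable planning figure, and 30 can no longer be presented as sufficient by power analysis.

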9.0 OUTCOMES AND SIGNIFICANCE

The intention of this study is to measure whether the use of a vapocoolant spray as an intervention increases the patient's satisfaction of IV insertion and decrease the patient's pain and/or perception thereof. This interventional study aims to show that the use of a vapocoolant spray prior to IV cannulation insertion will not only yield positive feedback from patients undergoing Nuclear Medicine scans but that such an intervention could change the traditional methods used for starting IV's in hospitalized patients. Furthermore, this study can be used to compare the use of a vapocoolant spray versus current practice which is not using a vapocoolant spray on IV insertions. This comparison will lead to awareness in pain management for IV insertions as well as determine if such a spray is cost effective and necessary.

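### Section 8.0 states no usable significance level, so the basis for 30 subjects cannot be verified, and no rule says whether pain, satisfaction or both must succeed

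*Combined protocol and SAP*

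**What the plan says.** The statistical plan is the single paragraph of Section 8.0. It describes the method as follows: "Analysis for this study is a descriptive statistic of a covariance using pre-procedure perception as the covariance". It then reports a power analysis, according to which "a minimum sample with a level of significance of 0.5 moderate effect size is 30 subjects". Power, sidedness, a numeric effect, a standard deviation and the outcome behind the calculation are not given. No other section states a significance level.

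Section 2.1 sets the primary purpose as finding out whether the spray "will increase the satisfaction with IV insertion as well as determine if pain of insertion is decreased". It then poses pain and satisfaction as two separate research questions. Section 9.0 again names both, and opens a statement of intended benefit with "This interventional study aims to show that the use of a vapocoolant spray prior to IV cannulation insertion". No section says whether one or both outcomes must succeed, or ranks them.

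On size, Section 6.1 says: "The target goal is 30 patients; however, researchers may recruit up to 80 patients". Section 8.0 treats 30 as a floor: "Our goal for this study is to exceed that sample size and have up to 80 participants". Section 6.1 also gives an accrual window: "This study will use a convenience sample of patients over a 4-month period".

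**The concern.** A significance level of 0.5 cannot be a working threshold for a claim of benefit. The correction matters because the level is an input to the calculation that produced 30. If 0.5 was actually used, the study is much weaker at a conventional level than the plan implies. If 0.05 was used and only the text is wrong, then 30 must rest on some other input that is not stated.

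The second gap is separate. With pain and satisfaction both in the primary purpose and no rule linking them, a significant result on either could be reported as success after the event, and the error rate of that claim would exceed the nominal level. Calling the analysis descriptive does not clearly remove the problem, because the same paragraph states a significance level and a power analysis, and Section 9.0 sets out to show a benefit.

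A smaller matter is that 30 is a target in one section and a minimum to be exceeded in another, and no sentence says what ends recruitment between 30 and 80.

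**Working it through.** **Inputs from the documents.** Level printed as 0.5, moderate effect size, minimum 30 (Section 8.0); maximum 80 (Sections 6.1 and 8.0); equal arms (Section 6.1); covariance analysis on pre-procedure perception (Section 8.0).

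**Assumptions.** Moderate effect taken as d = 0.5; power 80% where a size is solved for; two-sided tests unless stated; covariate-outcome correlation r of 0, 0.5, 0.7 or 0.87; correlation between the two outcomes 0.3 to 0.7.

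**1. Trying to reproduce 30.** Normal approximation, n per arm = 2(1 - r²)(z_level + z_power)²/d², rounded up and doubled.
- Two-sided 0.5, 80% power, r = 0: 2 × (0.674 + 0.842)²/0.25 = 18.4, so 19 per arm, 38 in total.
- One-sided 0.5, 90% power, r = 0: 2 × (0 + 1.282)²/0.25 = 13.1, so 28 in total.
- Two-sided 0.5, 80% power, r = 0.4 to 0.5: 32 to 28 in total.
- Two-sided 0.05, 80% power, r = 0: 2 × (1.960 + 0.842)²/0.25 = 62.8, so 126 in total (128 by the t-test).
- Two-sided 0.05, 80% power, one-sample or paired test: 32 (34 by the t-test), but this is not the two-group design.

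Several unstated combinations land near 30. None is given in the plan, so 30 is neither reproduced nor refuted.

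**2. What 80% power at a two-sided 0.05 would need.** Multiply 62.8 per arm by (1 - r²).

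| r (assumed) | per arm before rounding | total |
|---|---|---|
| 0 | 62.8 | 126 (128 by t-test) |
| 0.5 | 62.8 × 0.75 = 47.1 | 96 |
| 0.7 | 62.8 × 0.51 = 32.0 (just above 32, so 33) | 66 |
| 0.87 | 62.8 × 0.243 = 15.3 | 32 |

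The t distribution adds about two patients to each total. A size near 30 is reached only with r near 0.87.

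**3. Power at the planned sizes.** Noncentral t with noncentrality d√(N/4)/√(1 - r²) and N - 2 degrees of freedom, one fewer with the covariate. At N = 30, r = 0, the noncentrality is 0.5 × √7.5 = 1.37; at N = 80 it is 0.5 × √20 = 2.24.

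| N | level | r = 0 | r = 0.5 | r = 0.7 |
|---|---|---|---|---|
| 30 | 0.5 | 78% | 83% | 90% |
| 30 | 0.05 | 26% | 33% | 46% |
| 80 | 0.05 | 60% | 72% | 87% |
| 80 | 0.025 | 48% | 62% | 80% |

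These are powers for patients analysed. Section 6.1 adds: "If the participant has to have additional attempts by the researcher to start an IV, their study will automatically be excluded". No allowance for this is stated. If 10% or 20% were lost (assumed), 80 becomes 72 or 64, and the unadjusted 60% becomes 55% or 50%.

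**4. Two outcomes at 0.05 each, fixed size, no true effect.** Success on either = 1 - P(|Z1| < 1.96 and |Z2| < 1.96). With independent outcomes this is 1 - 0.95² = 9.75%. Simulation at N = 80 with outcome correlation 0.3, 0.5, 0.7 gives 9.5%, 9.2%, 8.4%; at N = 30 it gives 9.6%, 9.1%, 8.6%. If both must succeed, a false joint claim needs the unaffected outcome to reach significance, so it cannot exceed 5% at a fixed size. No split of the level is then needed.

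**The case against.** The 0.5 is very likely a slip, and nobody is shown to intend testing at 50%. That is fair: a reader might infer from the printed text that half of null comparisons would be declared significant, but the wording fits a misprint or a misplaced effect size better. What stands is that the plan contains no usable level, and that the number 30 depends on which explanation is true.

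The documents speak of a primary purpose and objective, not of primary outcomes, and the joining words in Sections 2.1 and 9.0 can be read as wanting both. Under that reading there is no inflation at a fixed size. But the rule is not written, and posing two separate research questions supports the other reading equally well.

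The stated covariance analysis may give more power than an unadjusted test. This also stands, which is why a range of r is shown. The plan gives no correlation from which to choose within it.

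A stronger reading of the open range is tempting: that investigators, who know the spray given and collect the scores, could stop when results look favourable, or that the Section 7.2 reviews act as interim efficacy looks. The documents do not support this. They plan no efficacy look and no results-driven stop. The reviews sit in a safety-monitoring section, Section 6.1 gives a 4-month period and a cap of 80, and Section 8.0 aims to go beyond 30. The target and minimum wordings describe the same range, so only a clarification is warranted.

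**Conclusion.** The point holds for the level and the success rule. Section 8.0 states no usable significance level or sidedness, and its basis for 30 cannot be verified. If d = 0.5 and a two-sided 0.05 were intended, 30 patients give 26% power unadjusted and 46% at r = 0.7; even 80 patients give 60% unadjusted and reach 80% only with a strong covariate. It does not follow that 30 was wrongly calculated, since the missing inputs could reconcile it. Without a success rule, a claim on either outcome carries a false-positive rate of about 8-10% instead of 5%, assuming 0.05 each and outcome correlation 0.3 to 0.7.

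The end of recruitment needs one clarifying line. The documents give no ground for attaching an error inflation to it. This should be settled before results are seen.

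**What to change.** 1. **Section 8.0, level and basis.** Replace 0.5 with the intended level and state sidedness. Restate the sample-size basis with the level, power, numeric effect size, outcome and covariate correlation actually used. Report the power that 30 and 80 analysed patients deliver; enrolling beyond the cap of 80 is not asked for.
2. **Section 8.0, success rule.** Prespecify one rule for pain and satisfaction: Holm, a fixed order chosen by the sponsor, or both required. Alternatively, declare the analysis descriptive, report estimates with confidence intervals and make no significance claim.
3. **Sections 6.1 and 8.0, one line.** Reconcile target with minimum and state that recruitment ends at a size or date fixed in advance, for example at 80 patients or the end of the 4-month period, whichever comes first, regardless of results.

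**Cost.** The changes are wording. Holm lowers per-outcome power at N = 80, d = 0.5, when only one effect is real: from 60% to about 48% unadjusted, from 72% to about 62% at r = 0.5, and from 87% to about 80% at r = 0.7. If both effects are real, the unadjusted figure falls to about 54%. A both-required rule needs no split, but one non-significant outcome defeats the claim. Under the example in item 3 the freedom to stop at 30 is lost, so accrual may exceed the Section 6.1 target by up to 80 - 30 = 50 patients, within the existing cap. Correcting the level may also oblige the sponsor to report low power for 30.
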